**Protocol Revision History**

**Initial Approval Version**

**Protocol v1.0**

**XX/XX/XXXX**

CONFIDENTIAL

---

## **A Introduction**

### **A1 Study Abstract**

Heart failure with reduced ejection fraction is a major global health problem. Every year, over 200,000 patients with heart failure receive pacing device implants for cardiac resynchronization therapy (CRT). However, one-third of the patients receiving CRT do not derive any benefit, a large population with refractory heart failure symptoms, high mortality, and tremendous healthcare costs. Our overall objective is to reduce heart failure by physiological individualized optimization of CRT pacing therapy guided by 12-lead electrocardiography (ECG).

Patients with heart failure and left bundle branch block benefit from CRT. This delivers pacing from right ventricle (RV) and left ventricle (LV) synchronously, the resultant ventricular electrical resynchrony leading to improved cardiac mechanics and acute hemodynamics, and subsequent reverse structural cardiac remodeling. This leads to reduced heart failure symptoms, hospitalizations and death. It is not known if programming an individually optimized RV-LV pacing offset to maximize electrical resynchrony can improve benefit from CRT.

The proposed study is a *randomized controlled trial* in patients undergoing implant of a CRT pacemaker/defibrillator device for clinical indications to evaluate benefit of RV-LV offset programming using ECG vs. standard nominal CRT programming without RV-LV offset. Patients receiving CRT devices will be randomized to either (A) active intervention of programming individualized RV-LV pacing offset to optimize ECG or to (B) active control of nominally programming CRT device without RV-LV offset. The patients will be followed to evaluate changes in heart failure endpoints including echocardiography, quality-of-life, functional performance and a blood biomarker.

### **A2 Primary Hypothesis**

Among patients receiving CRT, individualized RV-LV offset programming using ECG will result in improvement of heart failure endpoints.

### **A3 Purpose of the Study Protocol**

The results of this study will provide key mechanistic insights on the salutary effects of CRT on reverse cardiac remodeling. Physiologically-tailored individually-optimized CRT therapy would improve individual patient health by improving heart failure outcomes, and decrease the economic burden of refractory heart failure.

---

## **B Background**

### **B1 Prior Literature and Studies**

CRT can be lifesaving for heart failure patients with left bundle branch block (LBBB) and delayed electrical activation of the LV lateral wall. A pacing device is used to resynchronize the LV with electrical stimulation from implanted electrodes in the RV and in a LV coronary vein. CRT results in improved hemodynamics, beneficial reverse cardiac remodeling, and reduction in adverse outcomes like heart failure hospitalizations and death. Every year, over 200,000 CRT procedures are performed in heart failure patients worldwide. However, one-third of CRT patients fail to show a clinical response to CRT with a large implication for the quality and quantity of life, and economic healthcare burden. Non-response to CRT can be attributed to factors

like irreversible scarring of the heart muscle, absence of sufficient baseline electrical dyssynchrony that is amenable to CRT, suboptimal pacing electrode location, non-adherence to heart failure medications, competing cardiac arrhythmias limiting CRT delivery, and importantly, suboptimal CRT delivery due to non-individually optimized programming of the device.

**Optimizing RV-LV offset:** Previous techniques have been evaluated to individually program RV-LV offset to acutely optimize cardiac mechanics and hemodynamic performance with variable results. These methods included transthoracic echocardiography, gated SPECT perfusion imaging, invasive hemodynamic measurements, non-invasive digital photoplethysmography, and pacemaker lead sensors to measure peak endocardial acceleration. However, these techniques have failed on account of being cumbersome, non-standardized, lacking reproducibility, and failure to show improvement in clinical outcomes. Echocardiography to prospectively guide RV-LV offset optimization has not been demonstrated to be superior to simultaneous biventricular pacing without RV-LV offset. The aforementioned techniques for RV-LV offset optimization focus on acute mechanical and hemodynamic effects, without any evaluation of the resulting electrical resynchrony. The disappointing results have led experts to surmise that “an electrical problem requires an electrical solution”. We hypothesize that the salutary long-term effects of CRT are dependent on its impact on electrical rather than mechanical function.

**Commercial device algorithms for RV-LV offset:** Some device manufacturers have proprietary algorithms that use the RV-LV activation delay to make a recommendation for RV-LV offset programming. An adaptive algorithm for fusion of intrinsic right bundle branch conduction with LV only pacing has also been developed. These algorithms are based on relative local activation differences at the RV and LV pacing electrodes, and fail to incorporate activation of bulk of the heart muscle. Further limitations include inability to use these algorithms in setting of atrioventricular block or atrial fibrillation, and lack of validation to assess impact on clinical outcomes.

**ECG for optimizing RV-LV offset:** 12-lead ECG is a readily available tool to evaluate the electrical activation of the heart and has been retrospectively used to evaluate CRT in many studies (**Table 1**). It is, however, unclear whether the absence of ECG markers that predict a good response to CRT in an individual patient is due to remediable RV-LV offset programming, or is a result of non-programmable factors like electrode location and scarring of heart muscle; and how many patients will convert to a favorable ECG with RV-LV offset optimization.

**Table 1. Retrospectively using ECG after CRT to correlate with good clinical response.**

QRS duration	Lead V1 (or V2)	Lead I (or aVL)	Frontal plane QRS

 
• Shorter QRSd (absolute or indexed to baseline QRSd); QRSd shortening <math>\geq 25</math> ms
 
• QRS normalization
 
	
 
• R wave
 
• R/S <math>\geq 1</math>
 
• R wave amplitude (V1 or V2)
 
• Shortening of RS interval; RS shortening <math>\geq 10</math> ms
 
	
 
• S wave
 
• R/S <math>\leq 1</math>
 
• Reversal from positive to negative (lead I & aVL)
 
	
 
• Right axis deviation (from baseline left axis deviation)
 
• Vectorcardiogram QRS amplitude half way between LBBB and LV pacing
 

---

ECG has been evaluated prospectively in limited-scope small studies for RV-LV offset optimization. A shorter biventricular paced QRS duration (QRSd) has been associated with good CRT response. However, RV-LV offset programming to minimize the QRSd is not the most suitable method for RV-LV offset optimization. In a study by Vidal et al., RV-LV offset (-30 ms, 0, +30 ms) determined by shortest QRSd did not predict acute mechanical left ventricular resynchrony on tissue Doppler echocardiography. Other “summed” ECG parameters like 3-dimensional QRS area (voltage-time integral) are conceptually appealing but yet to be evaluated prospectively for CRT programming.

## **B2 Rationale for this Study**

We propose to study the heart failure effects of ECG-guided RV-LV offset optimization. In a randomized controlled trial, we will determine whether such individualized RV-LV offset optimization using ECG results in improved reverse cardiac remodeling and other heart failure endpoints.

# **C Study Objectives**

## **C1 Specific Aim**

**To determine the impact of individualized RV-LV pacing offset to optimize ECG on reverse cardiac remodeling and other heart failure surrogate endpoints:**

After CRT implant, we will *randomize* patients to either (A) active intervention of programming individualized RV-LV offset to optimize ECG or to (B) active control of nominally programming CRT device without RV-LV pacing offset. The *primary outcome* will be the reverse cardiac remodeling after 3-12 months, as assessed by LV end-systolic volume on echocardiography. The secondary outcomes will include quality-of-life (Kansas City Cardiomyopathy Questionnaire-12, KCCQ-12), functional performance (6-minute hall walk distance) and a prognostic biomarker (serum NT-proBNP).

## **C2 Rationale for the Selection of Outcome Measures**

The primary outcome is echocardiographic LV end-systolic volume. LV end-systolic volume is a reliable surrogate for clinical outcomes in clinical heart failure trials. Secondary outcomes include quality-of-life (KCCQ-12), functional performance (6-minute hall walk distance) and a prognostic biomarker (serum NT-proBNP). KCCQ-12 and 6-minute hall walk are standard metrics to assess quality-of-life and functional status in heart failure research. Serum NT-ProBNP strongly predicts improvement in cardiac function and favorable prognosis after CRT.

# **D Study Design**

## **D1 Overview or Design Summary**

Once the eligibility for the study is determined and patient has consented for participation, all study participants will undergo a baseline evaluation (within 6 weeks prior to 2 weeks after CRT device implant/upgrade). Echocardiogram, quality-of-life questionnaire, 6-minute hall walk, blood test, vital signs, ECGs, device interrogation and baseline demographic and medical history including chart review will be obtained. After CRT device implant/upgrade, participants will

---

undergo physiologic evaluations at various (up to 10 or more) RV-LV offset settings including ECGs and echocardiography. A randomized assignment using a random allocation table in REDCap will be used to program patients to (A) intervention or (B) control RV-LV offset setting. Patients will return for study follow-up between 3-12 months. Follow-up evaluations will include echocardiography, quality-of-life questionnaire, 6-minute hall walk test, blood test, vital signs, ECGs, device interrogation, and follow-up medical history including chart review. The patients will continue to be in extended follow-up through review of their medical charts till the end of the study (12 months from date of CRT implant/upgrade of the the last study participant).

**Treatment and control arms:** All study patients will receive standard of care clinically indicated medical and device therapy per their treating physicians. After implant of a clinically indicated CRT device or upgrade of a preexisting pacemaker or defibrillator device to CRT system, participants will be randomized 1:1 to treatment arms (A) active intervention of programming individualized RV-LV pacing offset to optimize ECG or to (B) active control of nominally programming CRT device without RV-LV offset. Of note, both intervention and control treatment are active FDA-approved CRT therapies and no investigational device or programming will be used, and no clinically indicated treatment will be withheld from any patient. At any time, if in the judgment of the patient's treating physicians or the research team, any treatment including CRT programming different from the study protocol is necessitated for clinical reasons, the appropriate clinically indicated changes will be made. At the end of the study, if the participant is clinically doing well and the programmed CRT settings are deemed clinically appropriate they will be retained, else the CRT programming may be changed as per standard of care.

Enrolled participants who have a failed or unsatisfactory LV lead implant will not be randomized.

## **D2 Subject Selection and Withdrawal**

### **2.a Inclusion Criteria**

1. Patients  $\geq 18$  years of age who are able to give consent.
2. Diagnosis of systolic heart failure.
3. Planned to undergo new CRT device implant (or upgrade of preexisting pacemaker or defibrillator device to CRT system) for standard clinical indications.
4. Expected to have over 95% heart beats resynchronized with CRT (absence of competing arrhythmias or plans to not immediately activate CRT therapy).

### **2.b Exclusion Criteria**

1. Unable to comply with the study follow-up.
2. Life expectancy  $\leq 1$  year.

### **2.c Ethical Considerations**

This is a patient-oriented research plan to optimize delivery of CRT in humans. Patients with heart failure undergoing clinically indicated CRT device implant/upgrade would form the study population. Human subjects receiving clinically indicated CRT are needed to evaluate the clinical impact of individualized RV-LV offset programming of CRT.

### **2.d Subject Recruitment Plans and Consent Process**

- Subjects will be enrolled from patients undergoing CRT device implant/upgrade at Barnes-Jewish Hospital. Patients will provide a signed informed consent prior to participation in the study. Enrollment will be voluntary. No children will be enrolled.
- Informed consent will be obtained by study personnel in person with ample opportunity to ask questions, consider options and decline participation. Participants will be educated about

---

the rationale of the research, logistics and follow-ups for the study, and risks associated with the study. The subjects will sign a Washington University Institutional Review Board approved informed consent document prior to being enrolled in the study. Only adult patients who are personally able to provide informed consent will be enrolled. If a patient is unable to consent, they will not be enrolled.

- No special vulnerable populations will be enrolled.

## **2.e Randomization Method and Blinding**

A 1:1 randomization scheme using a random allocation table in REDCap will be used. The patient and personnel assessing study outcomes will be blinded to the randomized assignment.

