### **F2 Statistical Methods**

The primary outcome of interest is the LV end-systolic volume. Secondary outcomes include quality-of-life (KCCQ-12), functional performance (6-minute hall walk distance) and a prognostic biomarker (serum NT-proBNP). We will perform **t-tests** to assess for differences in the % change from baseline in primary and secondary endpoints between treatment groups. Sub-analyses will evaluate for effect modification by subgroups based on ischemic vs. non-ischemic cardiomyopathy, sex, and magnitude of RV-LV offset based on ECG. We prespecify evaluation of the subgroup with ECG optimized RV-LV offset  $\geq 40$  msec. A two-tailed p-value 0.05 will be considered as threshold for statistical significance.

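### The protocol names baseline dyssynchrony and scar as drivers of CRT response, but describes no stratification and plans no adjustment for them: a loss of precision and interpretability, not bias

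*Combined protocol and SAP*

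**What the plan says.** - **Rationale.** A1 states that "Patients with heart failure and left bundle branch block benefit from CRT", and B1 that "CRT can be lifesaving for heart failure patients with left bundle branch block (LBBB) and delayed electrical activation of the LV lateral wall". Among the reasons for non-response, B1 names irreversible scar and "absence of sufficient baseline electrical dyssynchrony that is amenable to CRT".
- **Hypothesis.** A2 is not restricted to LBBB: "Among patients receiving CRT, individualized RV-LV offset programming using ECG will result in improvement of heart failure endpoints".
- **Eligibility.** Section 2.a asks for systolic heart failure, more than 95% of beats expected to be resynchronised, and "Planned to undergo new CRT device implant (or upgrade of preexisting pacemaker or defibrillator device to CRT system) for standard clinical indications". Neither 2.a nor 2.b contains a QRS-morphology or QRS-duration criterion.
- **Allocation.** D1 says "participants will be randomized 1:1 to treatment arms", and 2.e says "A 1:1 randomization scheme using a random allocation table in REDCap will be used". No strata, blocks or minimisation factors are mentioned.
- **Analysis.** F2 plans t-tests on percentage change from baseline, without covariates. On subgroups it says "Sub-analyses will evaluate for effect modification by subgroups based on ischemic vs. non-ischemic cardiomyopathy, sex, and magnitude of RV-LV offset based on ECG", and it adds the subgroup with an optimised offset of at least 40 msec. Conduction pattern and new implant versus upgrade do not appear.
- **Data.** D1, E2 and the study calendar (Table 2) include 12-lead ECGs, device interrogation and medical history with chart review at baseline.

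**The concern.** If baseline conduction and scar influence remodelling, as B1 says, they explain part of the variation in the primary outcome. An unadjusted t-test leaves that variation in the error term. Chance differences between arms in these factors then add noise to an estimate that is powered for only a 2-point difference.

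Interpretation is also affected. The intervention is electrical, and the population may include intrinsic LBBB, other conduction patterns and patients upgraded from a pacemaker, whose baseline rhythm may be RV-paced. If the overall result is null, a reader will ask whether benefit was confined to LBBB. The plan prespecifies no analysis by baseline conduction. Offset magnitude comes from the ECG evaluation after implant, so it is not a substitute.

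**Working it through.** **Inputs from the documents.** N = 200, so 100 per arm at 1:1. Target difference 2 points and SD 5, reading F1's 2 ± 5% as difference ± SD. Two-sided α 0.05, power 80%.

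**Assumptions.** LBBB share p of 50 to 90%. Prognostic gap D (difference in mean percentage LVESV change, LBBB versus other) of 1 to 5 points. The documents give neither.

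**1. The plan's own figure.** n per arm = 2(1.96 + 0.84)² × 5² / 2² ≈ 98.1, so 99 per arm and 198 in total. With 100 per arm, SE = 5√(2/100) = 0.71 and power = Φ(2/0.71 − 1.96) = 0.807. A noncentral-t calculation gives 0.804. F1 reproduces.

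**2. Chance imbalance without strata.** Probability that the LBBB share differs between arms by at least 10 percentage points (hypergeometric, 100 per arm):

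| LBBB share | P(difference ≥ 10 points) |
|---|---|
| 50% | 20% |
| 70% | 17% |
| 80% | 11% |
| 90% | 3% |

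Treating the arms as two independent binomials gives 18% at a 50% share and 14% at 70%. A 10-point imbalance shifts the estimate by 0.10 × D: 0.1 points at D = 1, 0.25 at D = 2.5 and 0.5 at D = 5. The last is a quarter of the 2-point target, but below one SE (0.71).

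**3. Type I error.** Simulation with 20,000 replicates, p = 70%, D = 5, total SD 5: the unadjusted t-test under unstratified allocation rejects in 0.050 of null trials. The imbalance is already covered by the standard error.

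**4. Gain from adjustment.** Variance explained R² = p(1 − p)D²/25; residual SD = 5√(1 − R²); power = Φ(2/(residual SD × √(2/100)) − 1.96).

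| LBBB share | D = 1 | D = 2.5 | D = 5 |
|---|---|---|---|
| 50% | 0.811 | 0.832 | 0.904 |
| 70% | 0.811 | 0.828 | 0.889 |
| 80% | 0.810 | 0.823 | 0.870 |
| 90% | 0.809 | 0.816 | 0.843 |

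This counts conduction pattern only. Any contribution from aetiology is not quantified.

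**5. Stratifying without adjusting.** At p = 70% and D = 5, R² = 0.7 × 0.3 × 25/25 = 0.21. Stratification reduces the true variance of the difference by the factor 0.79, but the t-test still uses the full variance. The effective critical value is 1.96/√0.79 = 2.21, a two-sided error of about 0.027; simulation gives 0.028. Simulated power is 0.835, against 0.889 with adjustment.

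**6. What a conduction interaction could show.** SE = 5√(2/(100p) + 2/(100(1 − p))). For a 2-point interaction, power is 0.29, 0.25, 0.20 and 0.13 at shares of 50, 70, 80 and 90%. Power of 80% needs an interaction of 4.0 to 6.6 points.

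**7. If the 2-point benefit existed only in LBBB.** The overall effect is 2p: 1.0, 1.4 and 1.8 points at shares of 50, 70 and 90%, with power 0.29, 0.51 and 0.72.

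**The case against.** The strongest reply is that nothing here is invalid. Randomisation makes imbalance a matter of chance, the t-test's standard error allows for it, and a 0.5-point shift needs both a tail event and a prognostic gap of one full SD. That stands. A reader might infer that unstratified allocation biases the comparison; step 3 shows it does not.

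A reader might also infer that the trial asks an LBBB question and leaves it unanswered. The documents do not support this. A2 addresses all CRT recipients, 2.c defines the population as clinically indicated implants and upgrades, and B1 faults device algorithms that cannot be used in atrioventricular block or atrial fibrillation. The LBBB statements explain why CRT works. Nor does eligibility admit every conduction pattern: the clinical-indication requirement limits it, although the protocol does not define that term. And the REDCap table itself is not shown, so one can say that no stratification is described, not that none exists.

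Further points stand in part. The aetiology subgroup is a rough proxy for scar, and baseline ECGs would allow a post hoc LBBB analysis. But a subgroup analysis does nothing for the precision of the primary test, and a post hoc analysis carries less weight than a prespecified one. It is also fair that an added interaction test would not settle whether benefit is confined to LBBB, given its power.

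**Conclusion.** The point holds as a low-cost improvement in precision and interpretability. The plan identifies influences on CRT response, collects the data from which conduction pattern and aetiology can be classified, and uses neither factor in the primary comparison. The gain at N = 200 runs from negligible (0.807 to 0.809 with a 1-point gap and a 90% LBBB share) to about 10 percentage points of power (0.904 with a 5-point gap and a 50% share). It depends wholly on the assumed share and gap and on F1's SD of 5. There is no case for changing eligibility or sample size on this ground, and no threat to type I error under the plan as described.

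**What to change.** 1. **F2, primary outcome.** Replace the unadjusted t-test with a linear model of treatment arm, adjusted for baseline conduction pattern (intrinsic LBBB versus other, the latter including RV-paced upgrades) and ischaemic versus non-ischaemic aetiology. Define both from pre-randomisation ECG, device history and chart review.
2. **F2, effect modifiers.** Add baseline conduction pattern, labelled exploratory, and state its limited power.
3. **2.e, optional.** State whether the allocation table is stratified. If it can still be changed, stratify by the same two factors with concealed, varying block sizes, and keep the adjustment in item 1, because stratification with an unadjusted t-test is conservative.

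**Cost.** Items 1 and 2 need a short F2 amendment, made before unblinding, and no extra patients. Both factors must be recorded in REDCap before randomisation. This needs care because the baseline window (−6 to +2 weeks) overlaps the window for CRT evaluation and randomisation (0 to +2 weeks), and E1 allows patients to be approached after implant. Item 3 adds some predictability of assignments for programming staff, since 2.e blinds only patients and outcome assessors.

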## **2.f Risks and Benefits**

- Participation in the research study requires a commitment of time by the participants. Every subject will undergo, both at enrollment and at the follow-up visit, evaluations including echocardiography, quality-of-life questionnaire, 6-minute hall walk test, blood test, vital signs, ECGs, device interrogation, and clinical history including chart review. After CRT implant/upgrade, participants will have a physiological assessment of various (up to 10 or more) RV-LV offset settings including ECGs and echocardiography. During study related CRT device evaluation, there is an extremely small risk of inducing cardiac arrhythmias that is similar to the risk entailed in standard routine clinical device interrogations. In the improbable event of an unstable cardiac arrhythmia, the patient will be immediately cardioverted using the implanted pacemaker/defibrillator or using an external defibrillator. A trained clinical electrophysiologist will be present in person during all study related interrogation and programming of CRT device.
- The alternative for human subjects to research participation is to not enroll for the study and undergo standard care with RV-LV offset programming at the discretion of the treating physician. The research question is a state of equipoise where it is not clear whether RV-LV pacing offset optimization using ECG is superior to nominally programming CRT device without any RV-LV offset. It is the intention of this research to investigate if there is any additional CRT benefit with individualized optimization of RV-LV offset.
- Potential benefits of the research to participants include close follow-up required for the trial post CRT system implant. Potential benefit of this research to other CRT recipients would be determination of individualized optimal RV-LV offset programming for maximizing CRT benefit and alleviation of heart failure.
- This outcome of this research will impact >200,000 heart failure patients who receive CRT every year, with more individually optimized delivery of CRT. This will be especially impactful for the large group of patients with refractory heart failure who currently derive no benefit from CRT. Improvement in CRT response would ultimately impact individual patient health by improving heart failure outcomes and reduce the economic burden on healthcare systems.

